6.7 Consent procedure

Participants will be approached via letter of invitation or telephone call by a member of the research team. They will be sent a Participant information sheet (PIS) and Informed Consent Form (ICF) and then if interested in participating they can contact the study team or will have a follow up phone call to see if they are interested. If they would like to be involved, they will receive a screening/telephone assessment as described above. If they meet inclusion criteria and wish to continue they may either be invited to meet or have a telephone call with an appropriately delegated member of the study team to allow the participant to ask questions, go through the consent procedure, and be informed of their right to withdraw at any stage. If consent is via telephone, the researcher will use a telephone script/consent form to ensure the process is documented appropriately. The contact will include a clear verbal explanation of the study (e.g., by talking through the PIS and the sections of the ICF). Only when the potential participant has had the opportunity to ask questions and had these answered satisfactorily, will they be asked to verbally confirm consent to participate. The telephone consent will be documented by the researcher/consent taker. Where possible, this consent process will be conducted in the presence of a witness e.g. another CRN practitioner or independent member of the clinical team.

If consent is collected face to face, a clear explanation of the study will be provided as above, the participant will be provided with time to ask any questions and once satisfied will be asked to complete the consent form.

6.8 Outcome measurement

Several outcome measures and data will be collected:

- Demographic characteristics and background information such as: age, sex, marital status, ethnicity, employment, diagnosis, duration of diagnosis and previous psychology input. This will be gathered by asking participants to complete a brief questionnaire once they have consented to take part in the study.
- Psychological outcomes collected through multiple pseudonymised self-reported questionnaire:
 - Generalised Anxiety Disorder Assessment (GAD-7) [23] to assess anxiety
 - Patient Health Questionnaire (PHQ-9) [24] to assess depression
 - Acceptance and Action Questionnaire (AAQ-II) [25] to assess psychological flexibility.
 - The RAND 36-item Health Survey 1.0 (SF-36) [26] to assess health-related quality of life (HRQoL).

These items will be measured at baseline (T1/pre-treatment); session 7 (T2/post treatment), and 8 weeks follow-up (T3/2-month follow-up).

- Medical outcomes:
 - Gastrointestinal/ HPN complications

- HPN requirements
- Hospital readmissions
- Opioid use
- Anti-depressant use

Medical outcomes will be collected accessing medical records at baseline and post follow up

A feedback evaluation questionnaire will also be used to measure the feasibility and acceptability of ACT intervention.

6.9 Withdrawal criteria

Participants will be allowed to withdraw from the study at any point. We will not collect any further data from this participant. However, data collected up to the point of withdrawal will be included in the analysis

7. Regulatory and Ethical Considerations

7.1 Study conduct

- The study will be conducted in accordance with the UK Policy Framework for Health and Social Care Research and other applicable guidance.
- The study will not commence until all regulatory approvals are in place, which will include Health Research Authority (HRA) Approval, Research Ethics Committee (REC) Approval and confirmation from local Research and Development that the Trust has capacity and capability to carry out the research.

7.2 Monitoring and audit

- The study will be subject to the standard procedures for monitoring and auditing of studies by the sponsor.
- Any changes to the protocol will be agreed with the sponsor prior to submission to NHS research ethics committee for review with the exception of where urgent safety measures apply.
- All staff working in the study will have completed appropriate training to undertake the duties delegated to them by the principal investigator such as ICH-GCP.

7.3 Protocol deviations

- Any deviations to the protocol will be reported to the sponsor within 24 hours of the occurrence to allow an impact assessment to be completed.
- Consideration will be given to the nature of the deviation, its causes, and the potential impact on the study.
- Where necessary, a deviation from the protocol may lead to an amendment to the protocol

7.4 Study progress reports

The PI and research team will submit progress reports to the Sponsor and funder: PORT & Bowel Research UK as requested and prior to submission to NHS REC, in accordance with the terms and condition of the study approval.

7.5 Stopping rules

Although no adverse events are anticipated, and it is not anticipated that the study will be stopped prior to its intended end-date. However, the study will be halted if:

- New information comes to light which means that the aims of the study are futile
- Safety issues come to light regarding the intervention
- Resources to conduct the study are no longer available
- Abuse of group guidelines, group guidelines include but are not exclusive to; remaining confidential, try to refrain from using mobiles, showing respect, listening and contributing where it feels comfortable to do so, joining from a secure space where participants will not be disturbed and participants will also be offered the opportunity to have telephone check ins where they can raise any concerns about any of the above or if anything else arises. Clinical judgements will also be made.
- If the study fails to recruit less than 10% of invited participants after 6 months of recruitment

8. Record keeping and data management

All information obtained from study participants will be treated as confidential and will comply with the requirements of the General Data Protection Regulations 2018 and the NHS Code of Confidentiality. All data collected will be stored on a secured (password protected) database with access available only to the chief investigator and study team responsible for handling and processing the relevant data. Any personal identifiable information will be stored separately from any interview content to ensure it remains anonymous. Study participants will never be identified by name when data or information are published or presented in the future.

9. Statistical analyses and data handling

Quantitative analysis

Descriptive statistics will be included for all psychological and medical outcomes. Further analysis is summarised in the table:

Objective	Method to measure this
Acceptability	The percentage of all patients randomised to the intervention arm minus deaths that complete the 2-month follow up. This will be compared to the percentage of controls (minus deaths) that complete the 2-month follow up. Completion will be defined as attendance at least 3 out of the 8 sessions. True completion will be defined as the number of participants who completed the whole intervention (all 8 sessions).
Feasibility	For those in the intervention group only: The results of the feedback evaluation questionnaire given after every intervention session.

Effectiveness	
The preliminary effect of the intervention will be estimated using the estimated mean difference between trial arms at post-treatment and 2 months follow up, adjusted for baseline scores, from analysis of covariance (ANCOVA). The analysis will be conducted using Stata 14 and an alpha level of 5%. This will be completed for all psychometric measures.
 
Results of the subgroup analysis will be described, comparing those with Chronic intestinal pseudo-obstruction (CIPO) against those non-CIPO to see whether the effectiveness or needs differ between these two groups.

---------------	---

Qualitative analysis

Qualitative interview audio recordings will be transcribed verbatim and all identifying information will be removed. Data will be analysed using reflexive thematic analysis [27-29]. Thematic analysis will include data familiarisation, initial coding, and sub-theme formation, and theme labelling.

10. Dissemination of Results and Publications

The final outcomes from the study will be communicated via presentations in scientific meetings and by peer reviewed publications. We will aim to publish the results approximately 12 months after completion of the study. The study and results may be promoted and publicised more widely via the Sponsor Trust's Research & Innovation website and on the PORT charities website.

11. References

4. Di Lorenzo, C., & Youssef, N. N. (2010, February). Diagnosis and management of intestinal motility disorders. In *Seminars in pediatric surgery* (Vol. 19, No. 1, pp. 50-58). WB Saunders.

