To assess the effectiveness, feasibility and acceptability of an online ACT based psychological intervention on psychological measures (distress, psychological flexibility, QOL and medical outcomes (described below in section 6) when compared to a control group who will receive treatment as usual (TAU).

4.2 Secondary Objective:

The study aims to recruit people with a diagnosis of GID, with a description of the results of those with CIPO against those non-CIPO to see whether the effectiveness or needs differ between these two groups.

5. Study Design

This study will be a pilot randomised controlled trial (RCT) with patients diagnosed with gastrointestinal dysmotility. Assessment of QoL of intestinal failure (IF) patients is very complex as IF is not only affected by the HPN treatment itself but also by the underlying disease and frequency of hospital readmissions. Therefore, a range of data will be collected including demographic characteristics, psychological outcomes, and medical outcomes, collected at different timepoints to allow for analysis (further detail is provided section 7.6 below).

Blinding of investigators or participants will not be possible in this study as participants and investigators will know whether participants had been allocated to the group or not. Participants allocated to the group intervention will be put into a group of 9-10 people. There will be maximum five rounds of the group intervention over the study period to meet sample size. The intervention is adapted from the Better Living with Illness group protocol [22] based on ACT. The group will be delivered over 7 weeks in weekly two-hour sessions, with a follow up 'reunion' at 8 weeks. A treatment manual has been adapted by the chief investigator who has received specialist training in ACT and previous experience of running this intervention online to people with long-term conditions. Each session utilises experiential exercises and metaphors to cover core ACT processes. Worksheets and guided mindfulness meditation exercises will be recommended to facilitate learning and encourage home practice. The intervention also covers problem solving skills, pacing, assertiveness skills and goal setting as they are important features of living with a long-term condition such as GID. An overview of the content of group sessions is provided in figure 1.

Figure 1, Session content of group

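### The recruitment halting rule in Protocol section 7.5 is inverted by a double negative: read literally, it halts the study at 10% uptake or more and is silent below 10%

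*Protocol*

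**What the plan says.** Section 7.5 of the Protocol says that early stopping is not expected, then introduces a list of triggers with "However, the study will be halted if". Four of them are matters of judgement: information that makes the aims futile, safety problems with the intervention, loss of resources, and abuse of the group guidelines. The fifth is numeric: "If the study fails to recruit less than 10% of invited participants after 6 months of recruitment".

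The denominator is the people invited. Section 6.7 describes how they are reached: "Participants will be approached via letter of invitation or telephone call by a member of the research team". Section 6.1 adds approaches at clinic appointments. Neither section says how many people will be invited, and no other section repeats the recruitment rule in different words.

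**The concern.** The sentence contains two negatives, *fails* and *less than*, which cancel. A study that fails to recruit less than 10% has recruited at least 10%. As worded, the rule therefore fires when uptake is adequate and stays silent when uptake is poor.

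This matters more than a slip in background text because the rule is operative and mandatory: the list says the study will be halted, not that halting will be considered. It is also the only trigger in section 7.5 that can be checked against a number. Section 7.3 requires any deviation from the protocol to be reported to the sponsor within 24 hours. A team that sensibly carries on at 10% or above departs from the approved wording, and a team that stops below 10% finds no support in this bullet.

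**Working it through.** No sample-size, power or error-rate formula applies. The check is a logical reading of the sentence.

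**Inputs**
- Consequence: the study is halted when a listed condition is true (section 7.5).
- Threshold: 10% of those invited, assessed after 6 months of recruitment (section 7.5).
- Number invited: not given in sections 6.1 or 6.7. I assume 100 for illustration only; the direction of the result does not depend on it.

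**Step 1: the rule as written.** Let R = recruited / invited at 6 months.

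Fails to recruit less than 10% = NOT (R < 10%) = (R ≥ 10%).

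The literal rule is: halt if R ≥ 10%.

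**Step 2: a low-recruitment rule.** With one negative removed (recruits less than 10%, or equally fails to recruit at least 10%), the rule is: halt if R < 10%.

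**Step 3: compare the two, with 100 assumed invited.**

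| Recruited | R | As written (R ≥ 10%) | Low-recruitment rule (R < 10%) |
|---|---|---|---|
| 3 | 3/100 = 3% | no halt | halt |
| 9 | 9/100 = 9% | no halt | halt |
| 10 | 10/100 = 10% | halt | no halt |
| 25 | 25/100 = 25% | halt | no halt |

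The conditions R ≥ 10% and R < 10% are complements, so the two versions disagree at every value of R, whatever the number invited.

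**Step 4: look for text that settles the direction.** The other four triggers in section 7.5 all describe something going wrong. A bullet that halts the study because recruitment went well would be the only exception. The intended direction is therefore clear from context, but it is an inference, because no sentence in the Protocol states it.

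**The case against.** The strongest reply is that this is a common over-negation with only one sensible reading, and that no investigator or sponsor would close a trial because recruitment reached 10%. That stands as to intent, and it limits the practical harm. The slip does not affect the randomisation, the baseline-adjusted ANCOVA or any result to be reported. It does not make the wording right: a mandatory threshold should mean what it says without the reader having to reverse it.

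Three stronger readings are tempting, and the document does not support them.

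- A reader might infer that a poorly recruiting study would have to continue. The literal text means only that this bullet would not stop it. The futility and resources triggers in the same list still could.
- A reader might take this as the only numeric threshold in the Protocol. It is the only one in the stopping rules. Section 9 also fixes completion at 3 of 8 sessions and an alpha of 5%.
- A reader might argue that a percentage of those invited is the wrong measure and that a minimum count tied to group size is needed. Section 5 sets groups of 9-10 and says "There will be maximum five rounds of the group intervention over the study period to meet sample size", but that is a ceiling on rounds. No allocation ratio and no number of invitations are stated, so any count would rest on assumptions. Uptake among those invited is a legitimate criterion for a pilot concerned with feasibility and acceptability, and the Protocol does not present it as a test of whether groups can be filled. Preferring a second criterion does not make this one an error.

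**Conclusion.** The rule is wrong as written. Its literal meaning is to halt at 10% uptake or more, the complement of the rule that was evidently intended, so the decision is reversed across the whole range of uptake. The reversal rests on no numerical assumption; the 100 invited is illustrative.

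The error is one of drafting, in an operative rule. The text does not show that the team meant to stop on good recruitment, or that the 10% figure itself is unsound. It needs correcting because it is the single numeric stopping criterion and nothing else in the Protocol puts it right.

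**What to change.** Replace the last bullet of section 7.5 so that, read with the lead-in to the list, it says: *the study will be halted if fewer than 10% of invited participants have been recruited after 6 months of recruitment*. This keeps the Protocol's threshold, denominator, timing and notion of recruitment, and changes only the direction. No minimum count needs to be added, and recruited need not be changed to randomised.

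The cost is a one-line amendment. Under section 7.2 it has to be agreed with the sponsor before submission to the NHS research ethics committee, so there is some administrative work. Nothing changes in recruitment procedures, data collection or analysis.

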Attendance will be recorded to assess recruitment and retention for the acceptability and feasibility part of the study and all group participants will be asked to complete a feedback form for each session attended of the intervention to assess effective components. Feedback will not be incorporated as the study progresses to retain intervention consistency for each participant as close as possible.

The study will utilise a mixed-methods design using quantitative standardised psychometric questionnaires to address psychological and quality of life outcomes, as well as a qualitative approach. The study will use face-to-face or telephone semi-structured interviews to explore participants experiences and views on the feasibility and acceptability of the intervention. These interviews will take place at one time point after the group intervention.

6. Detailed Plan of Investigation

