6.1 Recruitment procedure

The proposed recruitment strategy will involve screening the database at Salford Royal Hospital, Northern Care Alliance NHS Foundation Trust (NCAFT) for potentially eligible patients with gastrointestinal dysmotility. This search will be conducted by the research team working on the study and subsequently participants that fit the eligibility criteria will be sent a letter, approved by ethics, introducing them to the study and outlining what would be involved. Participants may also be approached during their HPN clinic appointment. A follow-up courtesy call 2-3 weeks after sending the letter may also be made by a member of the research team.

A telephone screening assessment will then be arranged with all interested participants for the therapeutic group programme to assess for suitability, to conduct a brief psychological assessment and check they meet inclusion criteria. During this phone call the research study will be discussed including the rationale in line with details provided on the participant information sheet and patients will have the opportunity to ask questions.

If after this telephone screening assessment with a clinical team member they meet inclusion criteria, and wish to continue, the research team will arrange a convenient time to obtain informed consent, via a consent form. Participants will be given a minimum of 24 hours to decide whether or not to take part. In some circumstances the participant may be asked to complete consent over the telephone. For example, in situations where to protect the safety of the participant and staff, it is not appropriate to bring the participant into a clinical setting for the consent process (e.g. during the COVID-19 pandemic). Participants will be randomised (using random number sequence methods) into one of two groups; the ACT intervention programme, or a control group receiving treatment as usual where they will not receive the psychological intervention during the study. Letters will be sent to GPs of all patients taking part in the study.

Those who do not give consent to be included in the study will still be able to access the Intestinal Failure Psychology team and standard NHS care and resources.

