All participants who provide consent will be asked to complete questionnaires at 3 timepoints (T1- baseline/pre-treatment; T2- week 7/post-treatment & T3 – 8 week-follow-up). These will be completed via paper, online, over the phone or email. The questionnaires will not have personal identifiable information on them but will be pseudonymised with a study participant number, of which only members of research team will have access to.

The second part of the study will involve semi-structured interviews performed by a suitably qualified member of the research team with training or experience to perform qualitative interviews. For the qualitative element of the study, participants will be able to register interest in the qualitative study and receive additional information about this part. Interviews will be conducted at a mutually agreeable time between the moderator conducting the interviews and the participant. If possible, they will try to accommodate this with their routine appointments at Salford Royal Hospital to make it easier for the participant to take part or alternatively over a video consultation.

6.2 Inclusion Criteria:

- 1) Has a diagnosis of Gastrointestinal Dysmotility
- 2) Age 18 years or above
- 3) Is fluent in English

6.3 Exclusion Criteria:

The participant may not enter the study if ANY of the following apply:

- 1) Insufficiently well to give consent or to take part
- 2) Currently receiving or due to start psychological therapy at another service or privately
- 3) Difficulties such that they are currently in receipt of on-going input from secondary care mental health services.
- 4) Substantial substance abuse difficulties
- 5) Severe and/or chronic mental health problems such as personality disorders where the interpersonal difficulties themselves are the required focus of an intervention
- 6) A learning disability, at such a level that specialist skills would be required to deliver an intervention.

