6.6 Study duration

The proposed project duration is expected to be 18 months from first receiving funding from PORT and Bowel Research UK. The start date for the study will be as soon as ethics and local C&C has been granted. The ACT intervention will occur in total over a 15-week period (7 weekly sessions plus an 8 week-follow up) with each session lasting approximately 120 minutes and it is expected to take between 25 minutes to complete the questionnaires. The final study visit for the group intervention

will be 31/05/2022. The qualitative interview phase of the study is expected to take participants between 30-60 minutes and interviews will be conducted once a participant has completed the intervention. All interviews will be conducted by October 2023. Writing up the results of this study is expected to be complete within 12 months after study end. Approximate end date 31/10/2023. Following this no further data collection will take place i.e. the last patient will have completed their last visit.

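### The acceptability measure compares the arms on completing the 2-month follow-up but defines completion by session attendance, so definition and comparison conflict

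*Protocol*

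**What the plan says.** Section 4.1 of the Protocol places acceptability in the primary objective, beside effectiveness and feasibility. The table in section 9 says how it is measured. For the ACT arm the measure is "The percentage of all patients randomised to the intervention arm minus deaths that complete the 2-month follow up". The comparator follows: "This will be compared to the percentage of controls (minus deaths) that complete the 2-month follow up". The next sentence defines the term: "Completion will be defined as attendance at least 3 out of the 8 sessions". A second tier, called true completion, requires all eight sessions of the intervention and is expressed as a number of participants, not a percentage.

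Four other places bear on this:

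- Section 6.6 describes the intervention as "7 weekly sessions plus an 8 week-follow up", which accounts for the eight sessions. Section 5 calls the last one a reunion.
- Section 6.1 describes the comparator as "a control group receiving treatment as usual where they will not receive the psychological intervention during the study".
- Section 6.1 also states "All participants who provide consent will be asked to complete questionnaires at 3 timepoints". Section 6.8 identifies the third of these, T3, with the 2-month follow-up.
- Section 5 says "Attendance will be recorded to assess recruitment and retention for the acceptability and feasibility part of the study".

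**The concern.** The row names one quantity, compares it between arms, and then defines its key word by something that only one arm can do. It also ties completion of a follow-up at a fixed time to a rule that can be met well before that time.

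In a pilot randomised trial, retention by arm is a core output. This row holds the only between-arm measure of acceptability: the session feedback forms go to group participants only, and the interviews explore experience of the intervention. Two analysts could follow the row in good faith and report different percentages for the ACT arm, and either 0% or a T3 return rate for controls. The trial is also unblinded (section 5), so unequal dropout is plausible, and a measure that mixes attendance with follow-up would not show it clearly.

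**Working it through.** The plan states no completion rate, target or sample-size figure for this measure, so there is no figure to reproduce. The check applies the written rule to each arm.

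**Inputs**

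- Sessions: 7 weekly + 1 at the 8-week follow-up = 8 (sections 5 and 6.6).
- Timing: 7 + 8 = 15 weeks from start to follow-up (section 6.6 gives the same 15 weeks).
- Sessions open to controls during the study: 0 (section 6.1).
- T3 questionnaires: requested in both arms (section 6.1) and labelled as the 2-month follow-up (section 6.8).

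**Step 1: controls.** The rule needs at least 3 of 8 sessions, and a control can attend 0 of 8. Read literally, control completion is 0 whatever the control arm's retention, and the between-arm difference reduces to the ACT attendance rate minus 0. It then says nothing comparative.

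**Step 2: ACT arm.** Session attendance and T3 return give four possible cases:

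| Attended ≥ 3 of 8 | Returned T3 | Complete by the written rule | Complete by T3 return |
|---|---|---|---|
| Yes | Yes | Yes | Yes |
| Yes | No | Yes | No |
| No | Yes | No | Yes |
| No | No | No | No |

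The rules disagree in the two middle rows. A participant who attends sessions 1 to 3 and then leaves has met the rule at week 3, which is 15 − 3 = 12 weeks before the follow-up point. Section 6.9 stops further data collection on withdrawal, so such a participant could have no T3 data and still count as completing.

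**Step 3: size.** Let N be the ACT participants randomised minus deaths, b the number who attended at least 3 sessions without returning T3, and c the number who returned T3 with fewer than 3 sessions. Then

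rate by the written rule − rate by T3 return = (b − c)/N.

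The documents give neither b nor c, so neither the sign nor the size can be derived. Only the scale per person can be indicated. If all five rounds of 9 to 10 people in section 5 were filled, N before deaths would be 5 × 9 = 45 to 5 × 10 = 50, and each net discordant participant would move the ACT percentage by 1/50 = 2.0 to 1/45 = 2.2 points. Five is a maximum, so fewer rounds would make each participant count for more.

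**Step 4: applying the rule to ACT only.** If controls are scored on T3 return and ACT on attendance, the difference compares two different behaviours. It would include (b − c)/N even if T3 return were identical in the two arms.

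**The case against.** The best defence is that the phrase about the 2-month follow-up already has a meaning common to both arms. Section 6.8 attaches that label to T3, section 6.1 asks every consenting participant for T3, and the effectiveness row uses the same time point for both arms in the ANCOVA. On this view the first two sentences of the row describe retention at T3. The two completion definitions are then a pair of adherence tiers for the intervention, as the mention of the whole intervention in the second suggests. The row would hold the right two measures and lack only labels. T3 return by arm could be counted in any case, because the questionnaires are collected in both arms.

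Much of this stands. A reader might infer from the row that the comparison is impossible, or that control completion must be reported as 0%. The documents do not support that, because the T3 reading is available and workable. Nor do they support any specific overstatement of retention: no attendance or return rates are given. It would also be too strong to say that unequal loss to follow-up would be undetectable, since the T3 data would show it if tabulated.

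What does not stand is that the row already says this. The definition directly follows the comparison, uses the same word and names no arm, whereas the Feasibility row beneath it is expressly limited to the intervention group. The row does not mention questionnaires, and section 5 links attendance records to retention. For the ACT arm, the week-8 reunion is a further candidate for what completing the follow-up means. Nor is this a detail left open for the statistical analysis plan: the protocol fixes a definition, and a plan using T3 return would have to depart from it.

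**Conclusion.** The point holds as a conflict between a stated comparison and the stated definition of its key term. Applied literally, the definition makes the comparison uninformative. Applied to ACT alone, it compares unlike things. The sensible reading, T3 return in both arms with attendance as ACT adherence, is probably what is meant, but the definition in the row contradicts it.

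The conclusion rests on the protocol's wording and on controls having no access to the sessions; it needs no assumed rates. The numerical effect on the reported percentages cannot be derived from the documents. The defect is confined to the acceptability part of the primary objective. The baseline-adjusted ANCOVA of the psychometric measures does not use this definition and is unaffected. Correction is warranted because a primary-objective measure should have one reading and the repair is small.

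**What to change.** Split the Acceptability row in section 9 into two measures.

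1. **Retention, both arms, one definition:** participants who returned the T3 questionnaires divided by all randomised to that arm minus deaths. Report the between-arm difference. Whether T3 counts as returned with one instrument or only with all of them, and the form of any confidence interval, can be left to the statistical analysis plan.
2. **Adherence, ACT arm only:** the proportion attending at least 3 of 8 sessions and the proportion attending all 8, each with all randomised to ACT minus deaths as denominator. This also gives the all-sessions count the denominator it lacks.

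Remove the link between the attendance rule and completion of the 2-month follow-up, and align the sentence in section 5 that ties attendance to retention.

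The cost is about two sentences in section 9 and a small edit in section 5. T3 questionnaires are already requested from everyone and attendance is already recorded, so no new data, visits or participant burden follow.
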